4.2.2. Adherence to Study Drug

The presumed total number of doses administered to a subject will be determined by the data collected on the drug accountability CRF using the following formula:

Total Number of Doses Administered =

$$\left(\sum \text{No. of Doses Dispensed} \right) - \left(\sum \text{No. of Doses Returned} \right)$$

If there are study drug bottles dispensed on or after the subject first met virologic failure criteria, these bottles will not be included in the calculation of adherence. If a bottle is dispensed and the bottle is returned empty, then the number of tablets returned will be entered as zero. If a bottle is dispensed but not returned (missing), the number of tablets taken from that bottle will be counted as zero.

The level of prescribed adherence to study drug will be determined by the total amount of study drug administered relative to the total amount of study drug specified by the protocol for a subject who completes treatment in the study.

The level of prescribed adherence will be expressed as a percentage using the following formula:

$$\text{Prescribed Adherence (\%)} = \left(\frac{\text{Total Amount of Study Drug Administered}}{\text{Total Amount of Study Drug Specified by Protocol}} \right) \times 100$$

Note: If calculated adherence is greater than 100%, the result will be set to 100%.

In this study, the total amount of LDV/SOF prescribed for 12 weeks of treatment would require 84 doses. Subjects who prematurely discontinue study drug for lack of efficacy (ie, virologic failure) will have the total amount of study drug prescribed calculated up to the first date when virologic failure criteria were met. For virologic failure confirmed by 2 consecutive measurements the date of the first measurement will be used.

Descriptive statistics for the level of prescribed adherence with the number and percentage of subjects belonging to adherence categories (eg, < 80%, ≥ 80 to < 90%, ≥ 90%) will be provided for the Safety Analysis Set.

No formal statistical testing is planned.

A by-subject listing of study drug administration and drug accountability will be provided separately by subject ID number (in ascending order) and visit (in chronological order).

4.3. Protocol Deviations

A summary of major protocol deviations will be provided by the Clinical Operations group for subjects in the Safety Analysis Set.

5. BASELINE CHARACTERISTICS

5.1. Demographics and Baseline Characteristics

The following subject demographic and baseline characteristics will be summarized by treatment cohort and overall using descriptive statistics (n, mean, standard deviation, median, Q1, Q3, minimum and maximum) for continuous data and by the number and percent of subjects for categorical data. Variables to be summarized include the following:

- age (on date of first dose of any study drug) as a continuous variable
- sex at birth (male, female)
- race
- ethnicity (hispanic or latino, not hispanic or latino)
- body weight (in kg)
- height (in cm)
- body mass index (BMI; in kg/m²) as a continuous variable and as categories (< 30 kg/m², \geq 30 kg/m²)
- HCV genotype
- cirrhosis (presence, absence)
- IL28B (CC; non-CC, with non-CC further broken down to CT, TT)
- baseline HCV RNA (\log_{10} IU/mL) as a continuous variable and as categories (< 6 \log_{10} IU/mL, \geq 6 \log_{10} IU/mL)
- baseline ALT as a continuous variable and as categories categories (\leq 1.5 \times ULN, $>$ 1.5 \times ULN)
- estimated glomerular filtration rate (eGFR) using the Cockcroft-Gault equation
- prior HCV treatment experience (treatment naive, treatment experienced)
- prior HCV treatment response for treatment-experienced subjects
- most recent HCV treatment regimen for treatment-experienced subjects
- fibrotest score as a continuous variable and fibrotest stage as a categorical variable

Age is calculated as the integer of age in years at first dose of study regimen.

eGFR will be calculated by the Cockcroft-Gault method using ideal body weight (IBW):

$$\text{eGFR}_{\text{CG}} (\text{mL/min}) = [(140 - \text{age (yrs)}) \times \text{IBW (kg)} \times (0.85 \text{ if female})] / (\text{serum creatinine (mg/dL}) \times 72)$$

IBW is estimated by the following equations:

- Males: $\text{IBW (kg)} = 50 \text{ kg} + 2.3 \text{ kg for each inch over 5 feet}$
- Females: $\text{IBW (kg)} = 45.5 \text{ kg} + 2.3 \text{ kg for each inch over 5 feet}$

The summary of demographic data and baseline characteristics will be provided for the Safety Analysis Set.

A by-subject demographic and baseline characteristics listing will be provided by subject ID number in ascending order.

A data listing of cirrhosis determination will be provided. A data listing will also be provided for subjects' prior HCV treatment and response.

5.2. Medical History

General medical history data will be collected at screening and listed only. General medical history data will not be coded.

6. EFFICACY ANALYSES

6.1. Primary Efficacy Endpoint

The primary efficacy endpoint is SVR 12 weeks after treatment discontinuation (SVR12) defined as HCV RNA < LLOQ (ie, < 15 IU/mL) 12 weeks after study drug cessation for the FAS. The COBAS® AmpliPrep/COBAS® TaqMan® HCV Test will be used to determine HCV RNA results in this study.

The 2-sided 95% exact confidence interval (CI) based on Clopper-Pearson method will be provided for the SVR12 rate.

6.2. Secondary Efficacy Endpoints

6.2.1. Definition of Secondary Efficacy Endpoints

Secondary efficacy endpoints include the following:

- The proportion of subjects who attain SVR at 4 and 24 weeks after treatment discontinuation, defined as HCV RNA < LLOQ (ie, < 15 IU/mL) 4 and 24 weeks after stopping treatment (SVR 4 and SVR 24)
- The proportion of subjects with HCV RNA below LLOQ (ie, < 15 IU/mL) by study visit
- HCV RNA (\log_{10} IU/mL) and change from baseline in HCV RNA (\log_{10} IU/mL) through end of treatment
- The proportion of subjects with virologic failure as the following:

On-treatment virologic failure

- HCV RNA \geq LLOQ after having previously had HCV RNA < LLOQ, while on treatment, confirmed with 2 consecutive values (note, second confirmation value can be posttreatment), or last available on-treatment measurement with no subsequent follow-up values (ie, breakthrough)
- $> 1 \log_{10}$ IU/mL increase in HCV RNA from nadir while on treatment, confirmed with 2 consecutive values (note, second confirmation value can be posttreatment), or last available on-treatment measurement with no subsequent follow-up values (ie, rebound)
- HCV RNA persistently \geq LLOQ through 8 weeks of treatment (ie, nonresponse)

Relapse

- HCV RNA \geq LLOQ during the posttreatment period having achieved HCV RNA < LLOQ at end of treatment, confirmed with 2 consecutive values or last available posttreatment measurement

6.2.2. Analysis Methods for Secondary Efficacy Endpoints

For analyses of HCV RNA < LLOQ (ie, < 15 IU/mL) by visit while on treatment and during the posttreatment (SVR) follow-up period, subjects will be assigned a value at each visit based on the categorical imputation rules described in Section 3.6.1. The 2-sided 95% exact confidence interval based on Clopper-Pearson method will be provided for the proportion. The overall category for “HCV RNA < LLOQ” will be split into the following 2 subcategories: “< LLOQ TND” for subjects with target not detected and “< LLOQ detected” for subjects with < LLOQ in tabular displays.

Graphs for the proportion of subjects with HCV RNA < LLOQ over time during treatment will be displayed.

Summary statistics will be presented for absolute values and change from baseline in HCV RNA (\log_{10} IU/mL) by visit through end of treatment (EOT). Imputation rules described in Section 3.6.1 will be used to assign HCV RNA values for missing values at a visit that are bracketed by “< LLOQ TND” and/or “< LLOQ detected”. Otherwise, a missing = excluded analysis will be performed.

For the SVR12 endpoint analysis, a summary table of the number and percentage of subjects with SVR12, virologic failure (VF), and Other will be created. All subjects who achieve SVR12 will be categorized as SVR12. Virologic failure will be descriptively summarized as “on-treatment virologic failure” and relapse (which will be broken down by study drug completed yes/no). Subjects who do not achieve SVR12 and do not meet criteria for VF will be categorized as Other. The denominator for relapse will be the number of subjects who had HCV RNA < LLOQ on their last observed on-treatment HCV RNA measurement; otherwise, the denominator will be the number of subjects in the FAS.

A concordance table between SVR12 and SVR24 will be provided. Subjects with both observed SVR12 and observed SVR24 data will be included for this analysis.

In addition, the proportion of subjects with ALT normalization (defined as ALT > ULN at baseline and ALT \leq ULN at each visit) will be presented by study visit. Tables for ALT normalization by visit will use methodology similar to the analyses of HCV RNA < LLOQ, but will use a missing = excluded analysis. Only those subjects with ALT > ULN at baseline (defined as the last ALT value collected prior to first dose of study drug) will be included in the analysis of ALT normalization.

7. SAFETY ANALYSES

Safety data will be summarized for subjects included in the safety analysis set. Summaries of safety data (treatment-emergent [TE] adverse events [AEs], TE maximum toxicity grades, changes from baseline in laboratory tests and vital signs parameters) will include all data collected on or after the first dose date of study drug through the last dose date of study drug plus 30 days for subjects who have stopped the study drug.

All safety data (except for laboratory tests with results that were cancelled by the lab) will be included in data listings based on the Safety Analysis Set.

7.1. Adverse Events and Deaths

7.1.1. Adverse Event Dictionary

Clinical and laboratory AEs will be coded using the current version of MedDRA. System organ class (SOC), high-level group term (HLGT), high-level term (HLT), preferred term (PT), and lower-level term (LLT) will be provided in the AE dataset.

7.1.2. Adverse Event Severity

Adverse events are graded by the investigator as Grade 1, 2, 3, or 4 according to toxicity criteria specified in the protocol. The severity grade of events for which the investigator did not record severity will be categorized as “missing” for tabular summaries and data listings. The missing category will be listed last in summary presentation.

7.1.3. Relationship of Adverse Events to Study Drug

Related AEs are those for which the investigator selected “Related” on the AE CRF to the question of “Related to Study Treatment.” Relatedness will always default to the investigator’s choice, not that of the medical monitor. Events for which the investigator did not record relationship to study drug will be considered related to study drug for summary purposes. However, by-subject data listings will show the relationship as missing.

7.1.4. Serious Adverse Events

Serious AEs (SAEs) will be identified and captured as SAEs if the AEs met the definitions of SAEs that were specified in the study protocol. SAEs captured and stored in the clinical database will be reconciled with the SAE database from the Gilead Drug Safety and Public Health Department before data finalization.

7.1.5. Treatment-Emergent Adverse Events

7.1.5.1. Definition of Treatment-Emergent Adverse Events

Treatment-emergent AEs (TEAEs) are defined as 1 or both of the following:

- Any AEs with an onset date on or after the study drug start date and no later than 30 days after permanent discontinuation of study drug
- Any AEs leading to premature discontinuation of study drug.

7.1.5.2. Incomplete Dates

If the onset date of the AE is incomplete and the AE stop date is not prior to the first dosing date of study drug, then the month and year (or year alone if month is not recorded) of onset determine whether an AE is treatment emergent. The event is considered treatment emergent if both of the following 2 criteria are met:

- The AE onset is the same as or after the month and year (or year) of the first dosing date of study drug, and
- The AE onset date is the same as or before the month and year (or year) of the date corresponding to 30 days after the date of the last dose of study drug

An AE with completely missing onset and stop dates, or with the onset date missing and a stop date later than the first dosing date of study drug, will be considered to be treatment emergent. In addition, an AE with the onset date missing and incomplete stop date with the same or later month and year (or year alone if month is not recorded) as the first dosing date of study drug will be considered treatment emergent.

7.1.6. Summaries of Adverse Events and Deaths

Treatment-emergent AEs will be summarized based on the Safety Analysis Set.

Summaries (number and percentage of subjects) of adverse events (by SOC and PT) will be provided using the safety analysis set as follows:

- All TE AEs
- Combined Grade 3 or 4 TE AEs
- Combined Grade 2, 3 or 4 TE AEs
- TE nonserious AEs occurring in at least 5% of subjects (this will be produced for ClinicalTrials.gov website)
- TE treatment-related AEs

- Combined Grade 3 or 4 TE treatment-related AEs
- Combined Grade 2, 3 or 4 TE treatment-related AEs
- TE SAEs
- TE treatment-related SAEs
- AEs leading to permanent discontinuation from the study drug
- AEs leading to interruption of the study drug

A brief, high-level summary of AEs described above will be provided by the number and percentage of subjects who experienced the above AEs. All deaths observed in the study will also be included in this summary.

Multiple events will be counted only once per subject in each summary. Adverse events will be summarized and listed first in alphabetic order of SOC and then by PT in descending order of total frequency within each SOC. For summaries by severity grade, the most severe grade will be used for those AEs that occurred more than once in an individual subject during the study.

In addition to the above summary tables, all TEAEs and TE treatment-related AEs will be summarized by PT only, in descending order of total frequency.

Data listings, with a variable indicating whether the event is treatment-emergent, will be provided for the following:

- All AEs
- All AEs of Grade 3 or higher
- SAEs
- Deaths
- AEs leading to premature discontinuation of study drug

7.2. Laboratory Evaluations

Laboratory data collected during the study will be analyzed and summarized using both quantitative and qualitative methods. Summaries of laboratory data will be provided for the Safety Analysis Set and will include data collected up to the last dose of study drug plus 30 days for subjects who have permanently discontinued study drug. The analysis will be based on values reported in conventional units. When values are below the LOQ, they will be listed as such, and the closest imputed value will be used for the purpose of calculating summary statistics as

specified in Section 3.7. Hemolized test results will not be included in the analysis, but they will be listed in by-subject laboratory listings.

A by-subject listing for laboratory test results will be provided by subject ID number and visit in chronological order for hematology, serum chemistry, and coagulation and other laboratory tests. Values falling outside of the relevant reference range and/or having a severity grade of 1 or higher on the Gilead Grading Scale for Severity of Adverse Events and Laboratory Abnormalities will be flagged in the data listings, as appropriate.

No formal statistical testing is planned.

7.2.1. Summaries of Numeric Laboratory Results

Descriptive statistics (n, mean, SD, median, Q1, Q3, minimum and maximum) will be provided for ALT, AST, total bilirubin, alkaline phosphatase, white blood cell (WBC) counts, neutrophils, lymphocytes, hemoglobin, platelets, reticulocytes, creatinine, INR, and creatinine clearance (calculated by the Cockcroft-Gault equation, using IBW) as follows:

- Baseline values
- Values at each postbaseline analysis window
- Change from baseline at each postbaseline analysis window

A baseline laboratory value will be defined as the last measurement obtained on or prior to the date/time of first dose of study drug. Change from baseline to a postbaseline visit will be defined as the visit value minus the baseline value. The mean, median, Q1, Q3, minimum, and maximum values will be displayed to the reported number of digits; SD values will be displayed to the reported number of digits plus 1.

In the case of multiple values in an analysis window, data will be selected for analysis as described in Section 3.8.3.

The number of subjects with hemoglobin < 10 g/dL and < 8.5 g/dL at any postbaseline visits (up to 30 days after the last dose of any study drug) will be summarized.

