1.4. Ledipasvir/Sofosbuvir Fixed-Dose Combination

Harvoni® (ledipasvir/sofosbuvir fixed-dose combination (LDV/SOF) combines two HCV specific-direct acting antiviral (DAA) agents into a single tablet for the treatment of chronic HCV infection. Sofosbuvir is a nucleotide analog that is a potent and selective inhibitor of NS5B-directed HCV replication, irrespective of HCV genotype. Ledipasvir is a novel HCV NS5A inhibitor that has demonstrated potent anti-HCV activity against genotypes 1 and 4 HCV infection. Harvoni® has been approved in the United States and Europe for the treatment of chronic HCV infection including treatment naïve and experienced patients with genotype 1.

For further information on the clinical pharmacology, virology, safety and efficacy of LDV/SOF, please refer to the current version of the Investigator's Brochure and US prescribing information.

1.5. Preliminary Results of Study GS-US-334-0154, Cohort 1

Preliminary results are available and presented below for Cohort 1: 10 subjects with estimated glomerular filtration rate (eGFR by Cockcroft-Gault) less than 30 mL/min within six months of screening, not on dialysis, treated with SOF 200 mg + RBV 200 mg daily for 24 Weeks. A review of the integrated safety, PK and efficacy from this first cohort demonstrate that SOF 200 mg + RBV 200 mg daily for 24 weeks is safe and relatively well tolerated.

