1.5.2. Safety

Sofosbuvir was generally well-tolerated and safe when administered with RBV in Cohort 1. Most adverse events (AEs) were mild to moderate in severity. There were two serious AEs (SAEs) of unstable angina and hyperglycaemic hyperosmolar nonketotic syndrome which were assessed by the investigators as not related to the study drugs. Neither event led to change in study drug administration. The most frequently reported AEs were anemia, headache, pruritus, and rash. Renal function and cardiac function were stable during treatment as assessed by eGFR, safety ECG and echocardiograms, respectively.

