Infant, ≤ 14 Days (hemolytic)	NA	NA	20.0 to 25.0 mg/dL 342 to 428 µmol/L	> 25.0 mg/dL > 428 µmol/L
Blood Urea Nitrogen	1.25 to 2.50 × ULN	> 2.50 to 5.00 × ULN	> 5.00 to 10.00 × ULN	> 10.00 × ULN
Hyperuricemia	>ULN to 10.0 mg/dL >ULN to 597 µmol/L	> 10.0 to 12.0 mg/dL > 597 to 716 µmol/L	> 12.0 to 15.0 mg/dL > 716 to 895 µmol/L	> 15.0 mg/dL > 895 µmol/L
Hypouricemia Adult and Pediatric ≥ 1 year	1.5 mg/dL to < LLN 87 µmol/L to < LLN	1.0 to < 1.5 mg/dL 57 to < 87 µmol/L	0.5 to < 1.0 mg/dL 27 to < 57 µmol/L	< 0.5 mg/dL < 27 µmol/L
Infant < 1 Year	N/A	1.0 mg/dl to <LLN- 57 µmol to <LLN	0.5 to < 1.0 mg/dL 27 to < 57 µmol/L	< 0.5 mg/dL < 27 µmol/L
Creatinine**	> 1.50 to 2.00 mg/dL > 133 to 177 µmol/L	> 2.00 to 3.00 mg/dL > 177 to 265 µmol/L	> 3.00 to 6.00 mg/dL > 265 to 530 µmol/L	> 6.00 mg/dL > 530 µmol/L

CHEMISTRY				
	Grade 1	Grade 2	Grade 3	Grade 4
Bicarbonate Adult and Pediatric ≥ 4 Years	16.0 mEq/L to < LLN 16.0 mmol/L to < LLN	11.0 to < 16.0 mEq/L 11.0 to < 16.0 mmol/L	8.0 to < 11.0 mEq/L 8.0 to < 11.0 mmol/L	< 8.0 mEq/L < 8.0 mmol/L
	NA	11.0 mEq/L to < LLN 11.0 mmol/L to < LLN	8.0 to < 11.0 mEq/L 8.0 to < 11.0 mmol/L	< 8.0 mEq/L < 8.0 mmol/L
Pediatric < 4 Years	NA	11.0 mEq/L to < LLN 11.0 mmol/L to < LLN	8.0 to < 11.0 mEq/L 8.0 to < 11.0 mmol/L	< 8.0 mEq/L < 8.0 mmol/L
Triglycerides (Fasting)	NA	500 to 750 mg/dL 5.64–8.47 mmol/L	> 750 to 1200 mg/dL > 8.47–13.55 mmol/L	> 1200 mg/dL > 13.55 mmol/L
LDL (Fasting) Adult	130 to 160 mg/dL 3.35 to 4.15 mmol/L	>160 to 190 mg/dL >4.15 to 4.92 mmol/L	> 190 mg/dL >4.92 mmol/L	NA
LDL (Fasting) Pediatric >2 to <18 years	110 to 130 mg/dL 2.84 to 3.37 mmol/L	>130 to 190 mg/dL >3.37 to 4.92 mmol/L	> 190 mg/dL >4.92 mmol/L	NA
Hypercholesterolemia (Fasting)	200 to 239 mg/dL 5.16 to 6.19 mmol/L	> 239 to 300 mg/dL > 6.19 to 7.77 mmol/L	> 300 mg/dL > 7.77 mmol/L	NA
	Pediatric < 18 Years 170 to 199 mg/dL 4.39 to 5.15 mmol/L	> 199 to 300 mg/dL > 5.15 to 7.77 mmol/L	> 300 mg/dL > 7.77 mmol/L	NA
Creatine Kinase	3.0 to < 6.0 × ULN	6.0 to < 10.0 × ULN	10.0 to < 20.0 × ULN	≥ 20.0 × ULN

*Calcium should be corrected for albumin if albumin is < 4.0 g/dL

** An overlap between the Grade 1 scale and the Lab's normal range for creatinine may result for Male subjects >70 yrs. Please follow the Gilead convention of grading any result within the LLN and ULN a 0.

ENZYMES				
	Grade 1	Grade 2	Grade 3	Grade 4
AST (SGOT)	1.25 to 2.50 × ULN	> 2.50 to 5.00 × ULN	> 5.00 to 10.00 × ULN	> 10.00 × ULN

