3.6.2. Outliers

Outliers will be identified during the data management and data analysis process, but no sensitivity analyses will be conducted. All data will be included in the data analysis.

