7.2.2.1. Treatment-Emergent Laboratory Abnormalities

Treatment-emergent laboratory abnormalities are defined as values that increase at least 1 toxicity grade from baseline at any postbaseline time point, up to and including the date of last dose of study drug plus 30 days. If the relevant baseline laboratory value is missing, any abnormality of at least Grade 1 observed within the time frame specified above will be considered treatment emergent.

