7.7. Other Safety Measures

A data listing will be provided for subjects who received dialysis during the study.

A data listing will be provided for subjects who become pregnant during the study.

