15.11.2.2.1	Grade 3 or 4 Treatment-Emergent Adverse Events	Safety Analysis Set
15.11.2.2.2	Grade 2, 3, or 4 Treatment-Emergent Adverse Events	Safety Analysis Set
15.11.2.3.1	Treatment-Emergent Treatment-Related Adverse Events	Safety Analysis Set
15.11.2.3.2	Treatment-Emergent Treatment-Related Adverse Events by Preferred Term	Safety Analysis Set
15.11.2.3.3	Grade 3 or 4 Treatment-Emergent Treatment-Related Adverse Events	Safety Analysis Set
15.11.2.3.4	Grade 2, 3, or 4 Treatment-Emergent Treatment-Related Adverse Events	Safety Analysis Set
15.11.4.1	Treatment-Emergent Serious Adverse Events	Safety Analysis Set
15.11.4.3	Treatment-Emergent Treatment-Related Serious Adverse Events	Safety Analysis Set
15.11.5.1	Adverse Events Leading to Premature Discontinuation of Study Drug	Safety Analysis Set
15.11.5.2	Adverse Events Leading or Interruption of Study Drug	Safety Analysis Set
15.11.6.1.1	Hemoglobin (g/dL) and Change from Baseline by Visit	Safety Analysis Set
15.11.6.1.2	Subjects with Postbaseline Hemoglobin < 10 g/dL and < 8.5 g/dL	Safety Analysis Set
15.11.6.1.3	Reticulocytes (x10 ³ /uL) and Change from Baseline by Visit	Safety Analysis Set
15.11.6.1.4	WBC (x10 ³ /uL) and Change from Baseline by Visit	Safety Analysis Set
15.11.6.1.5	Neutrophils (x10 ³ /uL) and Change from Baseline by Visit	Safety Analysis Set
15.11.6.1.6	Lymphocytes (x10 ³ /uL) and Change from Baseline by Visit	Safety Analysis Set
15.11.6.1.7	Platelets (x10 ³ /uL) and Change from Baseline by Visit	Safety Analysis Set
15.11.6.2.1	ALT (U/L) and Change from Baseline by Visit	Safety Analysis Set
15.11.6.2.2	AST (U/L) and Change from Baseline by Visit	Safety Analysis Set
15.11.6.2.3	Total Bilirubin (mg/dL) and Change from Baseline by Visit	Safety Analysis Set
15.11.6.2.4	Alkaline Phosphatase (U/L) and Change from Baseline by Visit	Safety Analysis Set
15.11.6.2.5	Creatinine (mg/dL) and Change from Baseline by Visit	Safety Analysis Set
15.11.6.2.6	Estimated Glomerular Filtration Rate by Cockcroft-Gault (mL/min) and Change from Baseline by Visit	Safety Analysis Set
15.11.6.3	INR and Change from Baseline by Visit	Safety Analysis Set
15.11.6.4.1	Treatment-Emergent Graded Laboratory Abnormalities	Safety Analysis Set
15.11.6.4.2	Treatment-Emergent Grade 3 or 4 Laboratory Abnormalities	Safety Analysis Set
15.11.7.1.1	Systolic Blood Pressure (mmHg) and Change from Baseline by Visit	Safety Analysis Set
15.11.7.1.2	Diastolic Blood Pressure (mmHg) and Change from Baseline by Visit	Safety Analysis Set

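### The planned creatinine and Cockcroft-Gault change tables have no rule for values taken after dialysis starts, so a subject who starts dialysis can be tabulated as less worsened, unchanged or improved

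*SAP*

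**What the plan says.** SAP 7.2.1 lists creatinine and "creatinine clearance (calculated by the Cockcroft-Gault equation, using IBW") among the parameters to be summarised at baseline, in each postbaseline window, and as change from baseline. The matching output in SAP Appendix 2 is Table 15.11.6.2.6, "Estimated Glomerular Filtration Rate by Cockcroft-Gault (mL/min) and Change from Baseline by Visit", on the Safety Analysis Set.

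Under SAP 7.2 these summaries run to 30 days after the last dose, and the only results kept out are those from hemolyzed samples. SAP 3.6.2, under the heading of outliers, adds that "All data will be included in the data analysis".

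The SAP foresees dialysis, in one place. SAP 7.7 says "A data listing will be provided for subjects who received dialysis during the study" (Listing 16.2.8.4). Nothing links that listing to the creatinine or eGFR tables.

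For graded abnormalities, SAP 7.2.2.1 counts "values that increase at least 1 toxicity grade from baseline at any postbaseline time point", and SAP 7.2.2.2 classifies each subject by the most severe postbaseline grade. The creatinine scale in Protocol Appendix 3 uses absolute limits, for example "> 3.00 to 6.00 mg/dL" for Grade 3.

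SAP 5.1 includes eGFR among the baseline characteristics but not dialysis status. Protocol 1.5 describes Cohort 1 as having eGFR "less than 30 mL/min within six months of screening, not on dialysis". Protocol 3 speaks of severe renal insufficiency, Protocol 4.2 sets only upper limits on creatinine clearance, and Protocol 4.3 has no exclusion for dialysis.

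**The concern.** Dialysis removes creatinine without restoring kidney function. After it starts, neither serum creatinine nor a clearance computed from it measures the subject's own renal function. The plan nevertheless pools such values with everyone else's. The subject with the worst renal outcome could then contribute a change near zero, or a gain, to the table meant to describe renal function on treatment.

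With 15 subjects planned in a single group, one value carries weight in a mean and can set the maximum. eGFR is also the measure from which renal function in Cohort 1 was judged: Protocol 1.5.2 reports that "Renal function and cardiac function were stable during treatment as assessed by eGFR, safety ECG and echocardiograms, respectively". A reader would naturally look at the same kind of table for Cohort 3.

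A related gap is that a subject already on dialysis at entry, if there is one, would not be identifiable in the baseline summary. The planned eGFR row would show a number without that context.

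**Working it through.** The documents give no figure on this point, so there is none to reproduce. The check uses the SAP's own equation.

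**Formula (SAP 5.1).** eGFR = (140 - age) x IBW x (0.85 if female) / (72 x Scr). Age and IBW are practically fixed over 12 weeks, so relative change = Scr at baseline / Scr at visit - 1, whatever moved the creatinine.

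**Assumed subject (not in the documents).** Man, 58 years, 69 inches, so IBW = 50 + 2.3 x 9 = 70.7 kg; baseline Scr 4.5 mg/dL. Baseline eGFR = 82 x 70.7 / (72 x 4.5) = 17.9 mL/min. Suppose renal function worsens so that Scr would reach 9.0 without dialysis, and dialysis brings the sampled value to 6.0, 4.5 or 3.0. The other subjects are assumed to change by -1 mL/min each. The mean for 15 subjects, k of them like this one with change x, is (-(15 - k) + k x) / 15.

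| Sampled Scr (mg/dL) | eGFR | Change x | Mean, k = 1 | Mean, k = 2 |
|---|---|---|---|---|
| 9.0 (no dialysis) | 8.9 | -8.9 | -1.53 | -2.06 |
| 6.0 | 13.4 | -4.5 | -1.23 | -1.46 |
| 4.5 | 17.9 | 0.0 | -0.93 | -0.87 |
| 3.0 | 26.8 | +8.9 | -0.34 | +0.33 |
| Post-dialysis value dropped | none | none | -1.00 (n = 14) | -1.00 (n = 13) |

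Three things follow.

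1. The displayed change runs from less worsened (-4.5) through unchanged to improved (+8.9, or +50%). All three understate the deterioration of -8.9.
2. The mean turns positive only if x exceeds 14 with one such subject, or 6.5 with two. Setting 17.9 x f / (1 - f) equal to those values, where f is the fractional fall in creatinine below baseline, gives f = 14 / (14 + 17.9) = 44% and f = 6.5 / (6.5 + 17.9) = 27%.
3. Dropping the post-dialysis value gives -1.00. That looks better than the all-data mean in the less-worsened case (-1.23), so exclusion alone is no remedy.

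**Median.** One subject of 15 can move the median only between adjacent ordered values of the other 14. With those 14 simulated as normal (mean -1, SD 3, assumed) and the dialysed subject at +10, the median is about -0.74, against -1.00 for a cohort without that value.

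**Graded table.** On the Appendix 3 scale, Scr 4.5 is Grade 3, 9.0 is Grade 4, 6.0 is Grade 3 and 3.0 is Grade 2. If any sample above 6.00 was taken before dialysis, the subject is counted as treatment-emergent Grade 4 and stays counted. If none was, no later dialysis-lowered value at or below 6.00 will count. Chemistry is drawn at Weeks 1, 2, 4, 6, 8, 10 and 12 and at post-treatment Week 4 (Protocol Table 6-2), so both situations are possible.

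**The case against.** The strongest reply is that the event is not hidden. Protocol 7.1.1 requires the condition that led to a procedure to be reported when it is an adverse event, and Protocol 7.1.3 requires laboratory abnormalities needing intervention to be recorded as adverse events. SAP 7.1.6 puts these into summary tables by system organ class and preferred term, including serious and Grade 3 or 4 events. The dialysis listing names the subject, and a pre-dialysis grade rise survives in the graded table. With 15 subjects, cross-checking is easy. All of this stands, and it limits the point to the numeric tables.

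It is also fair that the size is assumed throughout. A start late in treatment affects only the last windows, and a start after the last sample affects none.

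A reader might infer more than the documents support:

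- **That the primary safety endpoint fails.** Protocol 8.1.2 defines it by incidences of abnormalities. Mean change in eGFR is not an incidence, and the graded table keeps the worst grade at any visit.
- **That Cohort 3 is meant to include dialysed subjects.** The schedule footnote on subjects unable to pass urine is worded the same for Cohorts 1 and 2 (Protocol Table 6-1), and Cohort 1 was described as not on dialysis. Protocol 1.6.1 separates severe impairment from end-stage disease on hemodialysis. The text leaves the matter open and does not settle it.
- **That Cohort 3 will be declared renally stable from this table.** The Cohort 1 sentence is background, and nothing plans such a conclusion for Cohort 3.

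**Conclusion.** The point holds in limited form. SAP 7.2.1 and Table 15.11.6.2.6 apply no rule to creatinine or Cockcroft-Gault values after dialysis starts, although SAP 7.7 foresees dialysis on study. By the SAP's own equation, such a subject can be shown as less worsened, unchanged or improved in the windows after the start.

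The effect is confined to the numeric creatinine and eGFR summaries, mainly the mean and maximum, and to subjects whose grade had not risen before dialysis. The documents give neither a dialysis rate nor a creatinine distribution, so the size cannot be derived from them. The example shows a shift in the mean of about 0.3 to 1.2 mL/min for one subject of 15 (from -1.53 to -1.23 or to -0.34), under assumed creatinine values and an assumed change of -1 in the others. A change of sign with one subject needs a large fall in sampled creatinine.

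This is a cheap improvement worth making to a descriptive safety display. It does not threaten the efficacy analysis or the adverse event reporting.

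**What to change.** **SAP 7.2.1.** Present the creatinine and Cockcroft-Gault change tables using values before the first on-study dialysis. In the same table, show the number of subjects who started dialysis on study, counted as renal worsening. Keep the all-data table beside it, so that the general inclusion statement in SAP 3.6.2 is still met. Flag any subject on dialysis at baseline and list that subject separately for these two parameters.

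**SAP 5.1.** Add baseline dialysis status.

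**Protocol.** Reconcile Section 1.5 (Cohort 1 description), Section 3, Section 4.2 and Section 4.3 on whether dialysis at entry lies within the intended population. Which reading is right is for the sponsor to state.

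**Cost.** A few sentences, one derived flag and a table row or two, before the SVR12 database is finalised; later changes would have to be documented in the study report (SAP 1). The SAP already works this way elsewhere: hemolyzed results are listed but not analysed, and a count of subjects with low hemoglobin accompanies the numeric summaries.

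**Downside.** Dropping post-dialysis values is informative and can make the mean look better, so the reduced table must never appear without the count. The fix also assumes that dialysis dates are already collected for the listing; if they are not, they must be added to the data collection.
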